7.1.7. Additional Analysis of Adverse Events

The following treatment-emergent adverse events of special interest will be summarized by preferred term:

- Cardiac failure (narrow standardized MedDRA queries [SMQ])
- Cardiac failure (broad SMQ)
- Syncope, dizziness, or vertigo. MedDRA Version 19.1 PTs include dizziness, dizziness exertional, dizziness postural, fall, loss of consciousness, presyncope, vertigo, and CANVAS syndrome.
- Convulsions (narrow SMQ)

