1. INTRODUCTION

1.1. Background

HCM is an inherited cardiac disorder that occurs in approximately 1 in 500 people in the general population {[Maron et al 2013](#)}. The disease is usually caused by autosomal-dominant mutations in genes encoding contractile components of the cardiac sarcomere {[Maron et al 2012b](#)}.

Clinically, HCM is recognized as unexplained left ventricular (LV) hypertrophy (typically ≥ 15 mm thickness of the left ventricular wall) in the absence of other cardiac or systemic conditions capable of producing the magnitude of hypertrophy observed {[Gersh et al 2011](#)}. Typical symptoms include shortness of breath, angina, palpitations, fatigue and syncope. In a small percentage of patients, sudden cardiac death (SCD) may be the first presentation {[Elliott et al 2006](#)}.

HCM may present at any time from infancy to old age. It is most commonly diagnosed in the third and fourth decades of life, although the majority of patients who may satisfy the morphologic criteria for diagnosis are never brought to medical attention {[Maron et al 2012a](#)}. It is estimated that just over half of all patients clinically diagnosed with HCM present with symptoms that include shortness of breath and chest pain with exertion, palpitations, fatigue and syncope {[Adabag et al 2006](#)}. In the subset of patients who are symptomatic, the disease can progress along several discrete, but not mutually exclusive pathways {[Maron 2002](#)}:

- Diastolic dysfunction resulting in heart failure with preserved ejection fraction.
- Microvascular ischemia resulting in angina.
- Dynamic obstruction to blood flow in the LV outflow tract resulting in exercise limitation and syncope.
- Atrial fibrillation resulting in exacerbation of heart failure and increased risk of stroke.
- Malignant ventricular arrhythmias leading to sudden cardiac death or implantable cardioverter-defibrillator (ICD) shock.

There are currently no approved drugs for the treatment of HCM. The development of evidence-based novel treatments for HCM was identified in 2010 as an urgent need by the Working Group of the National Heart Lung and Blood Institute on “Research Priorities in Hypertrophic Cardiomyopathy” {[Force et al 2010](#)}.

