6.8. Assessments for Premature Discontinuation from Study

Please refer to Section 5.3.1, Dose Modification for Adverse Events, for down-titration and study drug interruption instructions.

If a subject permanently discontinues study drug dosing prior to Week 24, every attempt should be made to keep the subject in the study and continue to perform the required study-related follow-up and procedures until end of the double-blind treatment period. If this is not possible or acceptable to the subject or investigator, the subject will be withdrawn from the study.

If a subject permanently discontinues study drug dosing at or after Week 24, the 30-day Follow-up visit will be completed. Please refer to Section 6.6.1 for 30 day Follow-up visit details.

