7.2.2. Assessment of Severity

The severity grading of AEs will be assessed as described below:

Mild: Awareness of signs or symptoms, but easily tolerated; are of minor irritant type; no loss of time from normal activities; symptoms would not require medication or a medical evaluation; signs and symptoms may be transient, disappearing during continued treatment with study drug; symptoms which do not interfere with subject's daily activities.

Moderate: Discomfort enough to cause interference with usual activities; the study drug may be interrupted. Symptoms which may interfere with subject's daily activities; being within reasonable limits; not excessive or extreme; medium or average extent; study drug may be interrupted.

Severe: Incapacitating with inability to do work or do usual activities; signs and symptoms may be of systemic nature or require medical evaluation; the study drug may be stopped, and treatment for the event may be required. Events which interrupt subject's usual daily activities and may require medical intervention or treatment; study drug may be stopped.

7.3. Investigator Requirements and Instructions for Reporting Adverse Events and Serious Adverse Events to Gilead

Requirements for collection prior to study drug initiation

After informed consent, but prior to initiation of study drug, the following types of events should be reported on the eCRF: all SAEs and AEs related to protocol-mandated procedures.

Adverse Events

Following initiation of study drug, all AEs must be collected, regardless of cause or relationship, until 30 days after last dose of study drug, and be reported on the eCRF as instructed.

All AEs should be followed up until resolution or until the adverse event is stable, if possible. Gilead may request that certain AEs be followed beyond the protocol defined follow up period. AEs ongoing at the time of death are to remain ongoing unless it is confirmed that the event resolved at or prior to the death.

Serious Adverse Events

All SAEs (including deaths), regardless of cause or relationship, that occur after the subject first consents to participate in the study (ie, signing the informed consent) and throughout the duration of the study, including the protocol-required post treatment follow-up period, must be reported on the eCRF and to Gilead Drug Safety and Public Health (DSPH) as instructed. This also includes any SAEs resulting from protocol-associated procedures performed after informed consent is signed.

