2. TYPE OF PLANNED ANALYSIS

The Data Monitoring Committee (DMC) periodically reviewed safety data as specified in its charter.

This study was terminated by the Sponsor prior to the end of the double-blind phase, and therefore no subjects entered the OLE period. After all subjects have terminated the study, outstanding data queries have been resolved or adjudicated as unresolvable, and the data have been cleaned and finalized, the study blind will be broken and then the final analysis of the data will be performed.

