7.1.5. Treatment-Emergent Adverse Events

7.1.5.1. Definition of Treatment-Emergent

Treatment-emergent AEs are events that meet one of the following criteria:

- Any AEs with onset date of on or after the study drug start date and no later than 30 days after permanent discontinuation of study drug
- Any AEs leading to premature discontinuation of study drug.

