7.1.5.2. Incomplete Dates

If the date of onset is incomplete, then the month and year (or year alone if month is not recorded) of onset determine treatment emergent as follows. The event is treatment emergent if the month and year of onset (or year of onset) of the event meets both of the following criteria:

- The same as or after the month and year (or year) of the first dose of study drug
- The same as or before the month and year (or year) of 30th day after the date of the last dose of study drug

If the start date is missing and the stop date is on or before the date of the last dose of study drug plus 30 days, then the event is considered treatment-emergent.

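### SAP 7.1.5.2 counts an adverse event with no start date as treatment-emergent even if it stopped before the first dose; the wording of SAP 7.1.7 and 7.9 also needs clarifying

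*SAP*

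**What the plan says.** **Missing AE start date.** The onset criterion in SAP 7.1.5.1 is "Any AEs with onset date of on or after the study drug start date and no later than 30 days after permanent discontinuation". Protocol 8.6.2 likewise requires onset from first dose up to 30 days after last dose. For incomplete onset dates, SAP 7.1.5.2 compares the known month and year with both ends of that window. For a wholly missing start date it uses one condition: "If the start date is missing and the stop date is on or before the date of the last dose of study drug", with 30 days added, the event is treatment-emergent.

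**What is in the AE data before dosing.** Between consent and first dose, Protocol 7.3 says that "the following types of events should be reported on the eCRF: all SAEs and AEs related to protocol-mandated procedures". Other screening events go to medical history (Protocol 6.2.1).

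**Special-interest group.** SAP 7.1.7 labels one group with three concepts: syncope, dizziness and vertigo. It then states: "MedDRA Version 19.1 PTs include dizziness, dizziness exertional, dizziness postural, fall, loss of consciousness, presyncope, vertigo, and CANVAS syndrome". The other entries in that section are standardized MedDRA queries.

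**Deaths and defibrillator interventions.** SAP 7.9 summarizes, in one sentence, subjects who died or had an adjudicated appropriate intervention by an implantable cardioverter-defibrillator (ICD). The sentence ends with a restriction to subjects who have an ICD. Protocol 8.6.4 gives the same summary without the restriction. The safety criteria in the protocol synopsis attach the ICD qualifier to the interventions. SAP 7.10 declares no change on this point.

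**The concern.** The treatment-emergent flag feeds every treatment-emergent AE table. A rule that looks only at the upper end of the window can place a screening event, such as one caused by a baseline procedure, in the on-treatment counts.

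The other two passages raise a question of clarity. Protocol 1.1 says of this disease: "Typical symptoms include shortness of breath, angina, palpitations, fatigue and syncope". A special-interest table programmed strictly from the printed term list could leave out the concept that heads its own label. A death count read literally from SAP 7.9 could cover only part of the treated population.

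**Working it through.** No figure in the plan needs reproducing here. The check is logical.

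**1. Date rule.** The inputs are the onset criterion of SAP 7.1.5.1, the last sentence of SAP 7.1.5.2, and the fact that onset cannot be later than the stop date. For illustration, take first dose on Day 1 and last dose on Day 168 (an assumed value, equal to the Week 24 target day). The upper bound is then 168 + 30 = Day 198. AEs that led to premature discontinuation of drug are set aside, because SAP 7.1.5.1 makes them treatment-emergent (TE) in any case.

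| Stop date, start date wholly missing | Status under the onset criterion | SAP 7.1.5.2 as written | With a first-dose lower bound |
|---|---|---|---|
| Before Day 1 (e.g. Day -10) | Never TE: onset precedes first dose | TE (contradiction) | Not TE |
| Day 1 to Day 198 (e.g. Day 50) | Cannot be determined | TE, by stated convention | TE |
| After Day 198 (e.g. Day 230) | Cannot be determined | No rule stated | No rule stated |
| Ongoing or no stop date | Cannot be determined | No rule stated | No rule stated |

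For wholly missing start dates, the rule contradicts the definition in 1 of 4 patterns as written and in 0 of 4 with the lower bound. This counts logical cases and is not a rate. The patterns are not equally likely, and the documents give no frequencies.

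Two nearby rules suggest that the missing bound is a slip. The partial-date rule in the same section tests both first dose and last dose plus 30 days. SAP 7.6 excludes from concomitant medications any drug with a stop date before first dose.

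**2. Term list in SAP 7.1.7.** Eight preferred terms are listed. Of the three label concepts, dizziness and vertigo appear and syncope does not. Presyncope and loss of consciousness do appear.

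**3. SAP 7.9 against the other passages.** Take a death in a subject without an ICD. Protocol 8.6.4 counts it. SAP 7.1.6, item 11 of the brief AE summary, counts it. SAP 7.9 read literally does not. SAP 7.9 read in line with the synopsis does.

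**The case against.** The best defence of the date rule is that it will hardly ever matter. Before dosing, only serious and procedure-related events enter the AE form. Serious events are reconciled with the safety database (SAP 7.1.4). The analysis waits until "outstanding data queries have been resolved or adjudicated as unresolvable" (SAP 2). Any error would be an over-count, visible in the AE listing through its treatment-emergent flag. No formal safety comparison is planned (SAP 7). All of this stands and limits the size of the point. It does not make the rule consistent with the definition that it serves.

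A reader might infer more in three places, and the documents do not support it.

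- **That syncope will be lost.** The list is introduced by a word that can be read as open, and syncope is named in the label. SAP 7.1.6 tabulates all treatment-emergent AEs by preferred term, so syncope would be reported there. The table specifications and code are in a separate document (SAP 11) that is not available here. Whether Syncope is a separate preferred term in MedDRA 19.1 is also an assumption.
- **That deaths will be lost.** The placing of the ICD phrase is ambiguous, the synopsis suggests that it qualifies only the interventions, and SAP 7.1.6 counts deaths in any case.
- **That undated events which are ongoing, or stopped after last dose plus 30 days, are misclassified.** Their onset cannot be determined, so the missing convention is a gap in detail and not an error. Nor can they be presumed on-treatment. Serious events are reported "throughout the duration of the study, including the protocol-required post treatment follow-up period" (Protocol 7.3), and subjects off drug before Week 24 are asked to "continue to perform the required study-related follow-up and procedures until end of the double-blind treatment period" (Protocol 6.8; Protocol 5.3.1 says through Week 24). Counting all of them as treatment-emergent would also leave the rule's upper bound with no effect.

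**Conclusion.** The date rule is wrong as written. For an AE with no start date that stopped before first dose, SAP 7.1.5.2 gives a result that SAP 7.1.5.1 and Protocol 8.6.2 rule out. Confidence is high, because this follows from the text alone. How many records are affected cannot be estimated from the documents, but few are likely.

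The points on SAP 7.1.7 and 7.9 are requests for clearer wording, held with moderate confidence. The first is a visible mismatch between label and list. The second is an ambiguous modifier to be reconciled with the protocol. Neither is shown to produce a wrong result.

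Overall severity is minor. Descriptive safety tables could be touched; no efficacy result changes.

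**What to change.** 1. **SAP 7.1.5.2:** keep the upper bound and add to the last sentence a condition that the stop date falls on or after the date of first dose.
2. **SAP 7.1.7:** check the list against MedDRA 19.1 and, if Syncope is a separate preferred term there, add it explicitly.
3. **SAP 7.9:** reword so that the ICD phrase qualifies only the interventions, with deaths summarized for the whole safety analysis set. If the restriction on deaths is intended, declare it in SAP 7.10.

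The cost is three wording edits and small programming changes on data already collected. A few treatment-emergent flags may change. The edits are best made before the blind is broken, so that a change to a flag or a special-interest list cannot look data-driven.

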7. SAFETY ANALYSES

Formal statistical comparisons between treatment groups are not planned for safety analyses.

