7.1.6. Summaries of Adverse Events and Deaths

A brief summary of AEs will show, by treatment group, the number and percentage of subjects who (1) had any treatment-emergent AE, (2) had any treatment-emergent moderate or severe AE, (3) had any treatment-emergent severe AE, (4) had any treatment-emergent treatment-related AE, (5) had any treatment-emergent treatment-related moderate or severe AE, (6) had any treatment-emergent treatment-related severe AE, (7) had any treatment-emergent SAE, (8) had any treatment-emergent treatment-related SAE, (9) permanently discontinued from study drug due to an AE, (10) had dose reduced or temporarily interrupted due to an AE, and (11) died during study.

The number and percentage of subjects who experienced at least 1 TEAE will be provided and summarized by SOC, HLT and PT. For other AEs described below, summaries will be provided by SOC and PT, and/or by PT as indicated:

- All treatment-emergent AEs by severity
- All treatment-emergent AEs (by PT)
- All treatment-emergent treatment-related AEs (and by PT)
- All treatment-emergent serious AEs (and by PT)
- All treatment-emergent treatment-related SAEs (and by PT)
- All treatment-emergent AEs that caused permanent discontinuation from study drug
- All treatment-emergent AEs that caused temporary interruption of study drug
- All treatment-emergent AEs that caused dose reduction of study drug
- All treatment-emergent AEs that caused permanent discontinuation from study
- All treatment-emergent AEs leading to death

Multiple events will be counted once only per subject in each summary. For data presentation, SOC and HLT will be ordered alphabetically, with PT sorted by decreasing total frequency. For summaries by severity grade, the most severe event will be selected. In addition to the presentation by SOC and HLT, all treatment-emergent AEs will also be presented by preferred term only, ordered by decreasing total frequency.

In addition to the by-treatment summaries, data listings will be provided for the following:

- All AEs (with a flag indicating whether the event is treatment-emergent)
- SAEs (including deaths)
- Subjects who became pregnant during the study
- AEs leading to discontinuation of study or study drug
- Severe AEs
- AEs leading to temporary interruption of study drug
- AEs leading to dose reduction
- AEs leading to death

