11. SAP REVISION

Revision Date (dd month, yyyy)	Section	Summary of Revision	Reason for Revision
10 May 2017	All	Changed GS-6615 to eleclazine	Consistency with other eleclazine studies
	1	Updated introduction to indicate that synoptic report will be written.	Synoptic Report
	2, 3, 7	Removed reference to 2 database freezes	Synoptic Report
	3.1.3, 4.1	Removed reference to Per Protocol (PP) Analysis	Synoptic Report
	3.4, 6.3, 6.4.2	Removed subset analyses	Synoptic Report
	3.5, 6.5.2, 6.7	Removed references to sequential step-down testing; removed significance testing for exploratory endpoints	Synoptic Report
	3.7.6.4.1	Added details on calculation of MLHFQ if items are missing	Clarification
	3.7, 3.8.2, 7.2	Removed reference to laboratory data summaries	Synoptic Report
	4.3.2	Removed adherence to study drug summaries	Synoptic Report
	4.2	Removed reference to OLE; added week 24	Study stopped prior to OLE period
	3.1.3, 3.1.4, 3.8.2, 4.4, 7.1.3	Updated for consistency with new SAP template	Consistency with other studies
	6.3	Interaction term removed	FDA feedback
	6.3, 6.7	Removed reference to imputation methods	Synoptic Report
	6.3, 6.4.2, 6.7, 8	Removed reference to sensitivity analyses	Synoptic Report
	6.5.1	Removed some exploratory endpoint analyses	Synoptic Report
	6.6, 7.10	Updated	Synoptic Report
	7.1.7	Added summaries for AEs of special interest	Consistency with other eleclazine studies
7.5, 7.6	Updated definition of prior medications to medications taken prior to first dose and specified how to handle partial or missing start dates	Consistency with other eleclazine studies and clarification	
7.4	Removed CPET vital signs summary table	Synoptic Report	

	7.5, 7.6	Removed reference to medication summaries	Synoptic Report
	7.7.3	Removed ECG summary table	Synoptic Report
	7.9	Removed time to event summary table	Very few events
	8	Removed reference to summary tables	Synoptic Report
	Appendix 1, Appendix 2	Removed appendix with list of tables, figures, and listings and appendix with SAS code	Per current SAP template, appendices part of separate document

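### SAP 7.1.7: the preferred-term list for the special-interest group on syncope, dizziness and vertigo leaves out syncope itself

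*SAP*

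**What the plan says.** SAP 7.1.7 sets out four special-interest groups of treatment-emergent events, each to be summarized by preferred term. Three are defined by standardized MedDRA queries: cardiac failure (narrow), cardiac failure (broad) and convulsions (narrow). The fourth, "Syncope, dizziness, or vertigo", is defined by a list in the text: "MedDRA Version 19.1 PTs include dizziness, dizziness exertional, dizziness postural, fall, loss of consciousness, presyncope, vertigo, and CANVAS syndrome".

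SAP 7.1.6 separately provides general tables by treatment group. Treatment-emergent events are tabulated by system organ class, high level term and preferred term, and again by severity. In addition, "all treatment-emergent AEs will also be presented by preferred term only, ordered by decreasing total frequency". SAP 7 states: "Formal statistical comparisons between treatment groups are not planned for safety analyses".

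Two entries in the revision log (SAP 11) matter here. One, for 7.1.7, reads "Added summaries for AEs of special interest" and gives consistency with the other eleclazine studies as the reason. The other reads "Removed appendix with list of tables, figures, and listings and appendix with SAS code"; the reason given is that these now belong to a separate document.

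**The concern.** The group's name promises three kinds of event, and the list covers two of them by name. Syncope comes first in the name, and the protocol ties it to this disease: "Typical symptoms include shortness of breath, angina, palpitations, fatigue and syncope" (Protocol 1.1, which also lists syncope as a result of outflow tract obstruction).

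This group has no standardized query behind it, so the list is the only statement in the SAP of what the group contains. A programmer who takes it literally would produce a table titled with syncope that has no syncope in it. A reader of that table could take the absence to mean that no syncope occurred and would have to consult the general preferred-term table to find out. SAP 1 limits the summaries in the synoptic report to the main endpoints and the relevant exploratory and safety measures, so the few focused safety tables should be correct.

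**Working it through.** There is no design figure to reproduce. The check compares the group's name with its list and then follows each reading through to the tables.

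**Step 1. Count the listed terms (SAP 7.1.7).** They are (1) dizziness, (2) dizziness exertional, (3) dizziness postural, (4) fall, (5) loss of consciousness, (6) presyncope, (7) vertigo, (8) CANVAS syndrome. Total: 8. An exact match for syncope gives none; the nearest entry is presyncope, which is a different term.

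**Step 2. Compare the name with the list.**

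| Event in the group's name | Same term in the list? |
|---|---|
| Syncope | No |
| Dizziness | Yes |
| Vertigo | Yes |

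The list covers 2 of the 3. It therefore does not follow a convention of giving only terms beyond those in the name: under that convention dizziness and vertigo would also be absent. Listing presyncope and loss of consciousness indicates that syncope was meant to be covered.

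**Step 3. Look for the term elsewhere in 7.1.7.** The other groups (3 of 4) are set by query, and none names syncope. The documents do not give the contents of those queries, so nothing here relies on them. No other section gives a fuller list for this group.

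**Step 4. Follow each reading to the output.**

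| Reading of the list | Syncope in the special-interest table | Syncope by arm in the 7.1.6 tables |
|---|---|---|
| Closed: program the listed terms | Absent, whatever the number of events | Present |
| Open: the name counts, the list is illustrative | Present, if the programmer adds it | Present |

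At least three tables in 7.1.6 cover all treatment-emergent events by arm: system organ class/high level term/preferred term, by severity, and preferred term alone. The listing of all adverse events would also contain any syncope.

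**Step 5. Tests affected.** No formal safety comparison is planned, so the number is 0.

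**Step 6. After correction.** 8 + 1 = 9 listed terms, and the list covers 3 of 3 events in the name.

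**The case against.** The strongest reply is that the SAP introduces the terms with the verb *include*, which is ordinary open wording. Syncope is the first word of the group's name, so the list can be read as adding to a group that already contains it. The table specifications and code are in a separate document and may already have the term. This stands in part. It means the documents do not show that the final table will omit syncope. It does not make the definition sound: the list repeats the other two events in the name, so its silence on the third looks like a slip, and nothing in the SAP tells the programmer to add it.

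The second reply is that nothing is lost, because the general tables show syncope by arm and no test is planned. That is correct, and it sets the size of the point.

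A reader might be tempted to infer more, and the documents do not support it:

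- That the name and the list contradict each other. With open wording the text is incomplete and inconsistent, but the two can be reconciled.
- That the name calls for a fixed number of preferred terms. It names three kinds of event and no number of terms.
- That syncope was deliberately excluded or would be hidden from the report. Nothing suggests a choice to exclude it, and the 7.1.6 tables would show it.
- That the list must be closed to be valid. The documents do not show that any nine terms are complete, and a closed list could exclude other relevant terms.

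**Conclusion.** Wrong as written, minor: an inconsistency in an analysis definition. One term, the group's first-named event, is missing from the list of eight that defines the group. If the table is programmed from the listed terms, it cannot show syncope. The effect is confined to that one descriptive table. Reporting of syncope by arm elsewhere is intact, and no test is affected.

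The absence of the term is certain from the text. Its effect on the output is likely but not certain. It depends on the list being used literally and on the separate programming document not already supplying the term. It also assumes that reports of syncope are coded to a preferred term of that name; the documents do not reproduce the dictionary. No event rates are assumed.

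**What to change.** Insert syncope into the preferred terms in SAP 7.1.7, next to presyncope, and leave the rest of the bullet as it is. Then check the separate programming document and make the same addition if it uses the same list.

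Do this before unblinding. SAP 2 leaves room for it: once the data are final, "the study blind will be broken and then the final analysis of the data will be performed". Record the change in SAP 11.

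The cost is one added term. SAP 7.1.1 already has all adverse events coded in MedDRA, so no new data or coding are needed. Because this summary was added for consistency with the other eleclazine studies, their lists should be checked as well. They are not available here; if they share the omission, they need the same correction to stay comparable.
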